12.3 Laboratory Assessments

A complete series of laboratory evaluations (including hematology, serum chemistry, liver function tests [LFTs], thyroid evaluations, free testosterone and sex hormone binding globulin [SHBG for biological males only], urine/serum pregnancy, HCV antibody and reflex HCV RNA if positive, Immunoglobulin A tissue transglutaminase [IgA-TTG], and urinalysis) will be obtained during screening and subsequently according to the schedule of events ([Table-1](#) and [Table-2](#)). A positive IgA-TTG result for this test, will require a full review of celiac-related gastrointestinal symptoms (such as diarrhea, bloating, chronic unexplained abdominal pain), and other risk factors for celiac disease should be verified. These risk factors include: a family history of celiac disease, a personal history of Dermatitis Herpetiformis; Type 1 diabetes; impaired bone mineralization; malabsorption of micronutrients such as fat-soluble vitamins, iron, and potentially B12 and folic acid. Subjects previously enrolled prior to the addition of HCV or IgA-TTG testing in Amendment 2, will be asked if they are willing to have blood drawn for these specific tests. They may choose to refuse either or both of these additional tests and will be able to continue participation in the study regardless of either their refusal of consent or the results of the tests should they consent (the results will be used to support data analyses when the study is complete).

Quantitative serum pregnancy tests will ONLY be conducted at the initial screening visit, and again at baseline, to confirm non-pregnant status prior to dispensation of investigational product. Once on study, subjects will be expected to adhere to protocol required birth control requirements and serum pregnancy testing will not be done at regularly scheduled intervals. A serum pregnancy test will be ordered/Performed as follow-up to any positive and/or inconclusive urine test results (using unscheduled kit). The required clinical laboratory tests are listed in [Table-4](#). Pregnancy test results must be confirmed as negative prior to dispensing investigational product.

Additional tests and other evaluations required to establish the significance or etiology of an abnormal result or to monitor the course of an AE will be obtained when clinically indicated. In particular, if a clinically significant abnormal result is observed that is not resolved by the final study visit, tests will be repeated to document resolution or stability of the abnormality.

Specifically defined reflex testing, which will be performed for abnormal results, include:

- On-study TSH values above or below the upper or lower limit of normal (ULN or LLN), will result in reflex testing for Free T4 from the existing laboratory sample (when sample is insufficient, a re-draw is necessary).
- A positive HCV antibody will have HCV RNA processed from the existing laboratory sample, if possible (or on a re-draw if the original sample has insufficient material). The subject may not be enrolled if the HCV RNA result is detectable. Referral to a hepatologist or infectious disease specialist is recommended for consideration of antiviral treatment. Subject may be reconsidered, as appropriate, after treatment.

Table-4. Clinical Laboratory Assessments		
Serum Chemistry/Serology/Other	Hematology	Urine

 • Alanine aminotransferase • Albumin • Alkaline phosphatase • Aspartate aminotransferase • Bicarbonate • Blood urea nitrogen • Calcium (screening) • Chloride • Creatinine • Direct bilirubin • Estimated glomerular filtration rate • Gamma-glutamyl transferase • Glucose (random) • Indirect bilirubin • Lactate dehydrogenase • Potassium • Phosphate • Pregnancy • Sex hormone binding globulin (for biological males) • Sodium • Free testosterone (for biological males only) • Thyroid stimulating hormone (with reflex Free T4 if > ULN or < LLN) • Total bilirubin • Total protein • Uric acid • HCV antibody (if positive, then reflex HCV RNA; at screening only) • IgA-TTG (at screening only) 	
 • Hematocrit • Hemoglobin • Platelet count • Red blood cell count • White blood cell count • White blood cell differential 	
 • Urinalysis • Pregnancy

HCV = hepatitis C virus; IgA-TTG = Immunoglobulin A tissue transglutaminase.

12.4 Electrocardiogram Assessments

A standard 12-lead ECG will be obtained in triplicate (3 serial ECGs at least 1 minute apart, after the subject has been supine 5 minutes) according to the schedule of events ([Table-1](#) and [Table-2](#)); see the ERT Study Manual for ECG procedures. Electrocardiograms will be reviewed locally

for safety by the Investigator and/or their designee. The ECGs will be read centrally for the purpose of meeting the ECG study inclusion criteria, study withdrawal criteria and ECG intervals (PR, RR, QRS, QT, and QTcF using nomogram table), rate rhythm, and other clinically significant abnormalities (e.g., left ventricular hypertrophy, pathological Q-waves).

During the conduct of the trial, if a subject develops any other cardiovascular events noted as part of the exclusion criteria, the cardiovascular assessments in [Appendix 8](#) and [Appendix 9](#) are to be completed.

12.5 Physical Examination

A complete physical examination will be performed at the screening visit and subsequently according to the schedule of events ([Table-1](#) and [Table-2](#)). Physical examinations may be performed by physicians or mid-level providers, such as advanced practice nurses and physician assistants, if they are appropriately licensed and credentialed to perform these examinations in accordance with local requirements and/or regulations.

12.6 Vital Signs

Blood pressure and heart rate will be taken while seated for at least 5 minutes. Temperature may be taken by any standard method (e.g., oral, tympanic, rectal, etc.).

Vital signs (blood pressure, heart rate, respiration rate, body temperature, and weight) will be obtained at the screening visit and subsequently according to the schedule of events. The height, weight, and BMI will be recorded only at screening. Weight will be obtained at the screening visit and subsequently according to the schedule of events ([Table-1](#) and [Table-2](#)).

12.7 Subjective Opiate Withdrawal Scale

The SOWS is a self-administered scale for grading opioid withdrawal symptoms. It contains 16 symptoms whose intensity the subject rates on a scale of 0 (“not at all”) to 4 (“extremely”). The instrument can be found in [Appendix 4](#). In this study, subjects will complete SOWS daily for 14 days, starting at the Off-Treatment visit and continuing through the washout and safety follow-up period to the Last Visit on the study. **For subjects who discontinue study drug early (including in-between study visits), the change in subject status to “Off-treatment” in the Trialogics portal should be made immediately as the site becomes aware of discontinuation;** SOWS entries provide valid information ONLY if they are collected in the first 14 days off-treatment.

12.8 Brief Neurological Assessment

In order to monitor any potential CNS related side effects, a brief neurological assessment will be conducted according to the schedule of events ([Table-1](#) and [Table-2](#)), as well as a focused neurological medical history which will be obtained at screening. Minimally, the following neurological criteria should be assessed: mental status, motor exam, sensory exam, coordination, and gait.

13 STATISTICAL EVALUATION

As a companion to this protocol and to provide a more detailed explanation of the statistical methodology to be used for this study, a SAP will be developed prior to locking the database and before unblinding the randomization.

13.1 Sample Size and Power

The original planned sample size of approximately 240 subjects (120 per group) is based on assumed responder percentages for placebo and NAL ER of 25% and 45%, respectively. These responder percentages represent estimates based on the Week 10 data from the TR03 study. The power for the sample size estimate is set at 90% with a 2-sided significance level of 0.05.

In the TR03 study, all those who achieved a 50% reduction in WI-NRS itch also achieved at least a 4-point reduction in itch from baseline, matching the responder definition for the current study. Results for all treated subjects showed a response rate for the 50% reduction criterion of 6 of 18 (33.3%) for the NAL ER 162 mg treatment group versus 4 of 22 (18.2%) for placebo (for those

who completed the 10-week study, results were 6 of 12 [50.0%] and 4 of 20 [20.0%]). Of note, the placebo response in TR03 falls on the lower end of the expected range for endpoints that reflect PRO endpoints in neurologically-mediated diseases such as pain or psychiatric disease. Studies in these areas frequently show placebo responses in the 20% to 30% range and sometimes as high as 40%²⁹. The role of placebo response in dermatology has been increasingly documented and recognized in recent years³⁰. Given the small size of the TR03 dataset, and the variability of placebo response in comparable disease states, the estimate of placebo response for TR11 was set at 25%.

The NAL ER 162 mg responder rate is estimated at 45% for TR11, versus the 33.3% observed in TR03, for the following reasons: firstly, the TR03 endpoint was set at Week 10, and it is expected that the additional 4 weeks of active therapy will likely increase the response rate in this treatment arm. Secondly, experience from the TR03 study indicated that with close follow-up and guidance during the titration period, subject drop-out due to early symptoms associated with opiate initiation can be decreased, although not eliminated. Given that the completer's analysis in TR03 demonstrated a response rate of 50% (again acknowledging the small size of the cohort), increasing the number of subjects completing the study is expected to result in a somewhat higher all-treated response rate in the active arm than was seen in TR03.

To address the concern of the reliability of the estimates of treatment effectiveness from the TR03 study, an adaptive mid-course Sample Size Re-Estimation (SSRE) procedure was introduced in Amendment 2, Protocol v3.1, when less than 10 subjects had been randomized. The analysis was to be performed after 50% of subjects (N=120) had either completed the Week 14 primary endpoint assessment or terminated the study early. Due to COVID 19-related delays, and because the key boundary for the lower margin of the SSRE did not differ if conducted at 45% of subjects, the SSRE was performed based on the Week 14 data for 109 subjects (including pre-Week 14 discontinuations). The analysis was performed as planned by a single, external, unblinded statistician, and was presented and discussed at a closed session of the study DSMB. Based on the DSMB recommendation, the sample size for this study is

being increased to 360 subjects based on the SSRE conditional power which fell within the ‘promising zone’ as defined by Mehta and Pocock. (see [Section 13.4.6.4](#) for details).

13.2 Randomization

A randomization schedule will be computer-generated before the start of the study. After all screening procedures are performed and results of screening tests are available, eligible subjects will be activated in the IWRS, and assigned randomly on a 1:1 basis to the following treatment groups:

- Arm A: 162 mg NAL ER
- Arm B: Placebo

Randomization will be performed by the IWRS. Subjects will be stratified by site.

13.3 Statistical Analysis Sets

13.3.1 *Modified Intent-to-treat Population*

The MITT population will consist of all randomized subjects who have received at least a single dose of investigational product. The MITT population will be used for all efficacy analyses. In the event of a discrepancy between the randomized treatment and the actual treatment received, subjects will be analyzed for efficacy according to their randomized treatment assignment.

13.3.2 *Per-protocol Population*

The per-protocol (PP) population will include all subjects in the MITT population without any major protocol deviations that could have influenced the validity of the data for the primary efficacy variable. The deviations can include, but are not limited to:

- Key inclusion/exclusion criteria not satisfied
- Use of prohibited concomitant medications (this category includes those with anti-itch activity, see [Section 10.6.4](#))
- Inadequate investigational product compliance, which will be determined before breaking the blind

The subjects to be excluded from the PP population will be identified in a blinded fashion and documented in a memo prior to the database lock and unblinding.

13.3.3 *Safety Population*

The safety population will consist of all randomized subjects who have received at least a single dose of investigational product. The safety population will be used in all safety analyses. In the event of a discrepancy between the randomized treatment and the actual treatment received, subjects will be analyzed according to the treatment they actually received.

13.4 Statistical Methods

13.4.1 General Principles

Summary statistics will be presented by treatment group. For continuous variables, unless otherwise stated, the number of available observations (n), mean, standard deviation, median, and range will be provided. For categorical variables, the number and percentage in each category will be displayed.

For the open-label extension period, summary statistics will be presented by treatment group (as per the double-blind period) and overall as a single group. Only descriptive statistics will be displayed for open-label extension period.

Assessments of change from baseline to post-baseline will include only those subjects with both baseline and post-baseline measurements. Baseline for WI-NRS is derived as the average of the responses on the 7 days prior to the first dose of investigational product. For other variables, the last value of a variable taken before the first dose of investigational product will be used as the baseline value.

A more detailed description of study analyses will be presented in the SAP.

13.4.2 Missing Data

Unless otherwise specified, missing or dropout data will not be imputed for the purpose of data analysis. For the primary and secondary endpoint analyses, multiple imputation will be utilized to estimate missing data; details are discussed in [Section 13.4.6](#) and will be elaborated upon in the SAP.

13.4.3 Demographic and Baseline Characteristics

Demographics and baseline disease characteristics, medical history, laboratory data, and physical examination findings will be summarized descriptively by treatment group.

13.4.4 Subject Disposition

Subject disposition will be summarized, including the reasons for discontinuation. The number of subjects in each analysis population will be displayed and an accounting of exclusions from each study population will be provided.

13.4.5 Concomitant Medications

Concomitant medications will be tabulated by Anatomic and Therapeutic Class of World Health Organization (WHO) drug, preferred term, and treatment group. For the purposes of data collection, a medication's usage will be considered concomitant if it was started within 14 days prior to Informed Consent and continued after administration of the investigational product. If the start date is missing, it will be assumed that the medication was used concomitantly.

Concomitant medications should be collected from 14 days prior to the signing of consent. Beginning at the screening visit, and continuing for the duration of the study, subjects must be instructed to record any new concomitant medication use on the Subject Medication Log. Subjects should bring the log to every clinic visit and refer to it during telephone contacts. The Subject Medication Log should be retrieved for review by study staff at each visit prior to re-dispensing it (or issuing a new log) to the subject.

13.4.6 Efficacy Analyses

13.4.6.1 Analysis of Primary Endpoint

The proportions of NAL ER and placebo subjects who meet the primary endpoint definition of response (a ≥ 4 -point reduction of the 7-day average WI-NRS from baseline to Week 14) will be compared using a logistic regression model, with baseline WI-NRS as a covariate and the pooled site as a random effect. Subjects with missing Week 14 WI-NRS data and/or who withdraw prematurely prior to Week 14 will be imputed to have non-responder status in the primary mixed-effects model. The baseline covariate was selected because it is a clinically meaningful factor related to response to treatment. Study sites, pooled where appropriate, will be treated as a random effect to account for possible correlation between subjects within a site. Sites will be evaluated to ensure that both treatment groups are reasonably represented prior to inclusion in the analysis. Smaller sites will be combined regionally for Europe and the USA, with conditions for pooling described in the SAP.

To assess the impact of the above “treatment failure” rule, the missing data strategy will employ the multiple imputation (MI) procedure, as well as the completers case (i.e., omitting subjects with missing outcomes) analysis. Multiple imputation was chosen because single imputation cannot reflect the sampling variability under one model or the uncertainty for the correct model. For sensitivity analyses, the above logistic regression model will be re-analyzed using MI to impute missing data, followed by the completers case analysis.

The analysis will be based on the MITT population. Details will be described in the SAP. For all open-label visits, descriptive statistics will be displayed by treatment.

In addition, the primary endpoint will be analyzed using the PP population.

13.4.6.2 Analysis of Secondary Endpoints

All secondary endpoints will be analyzed using the MITT population. The change from baseline in continuous endpoints (WI-NRS, ItchyQoL, PROMIS Sleep Disturbance Short Form 8a) up to Week 14 will be analyzed based on a mixed model for repeated measures analysis that includes the fixed effects of treatment, visit, treatment by visit interaction, and baseline value. The main treatment comparison of interest is at Week 14. For PAS, individual items will be presented with counts and percentages for categories by treatment group and visit; for excoriations/crusts, a logistic regression analysis will be performed for data at Week 14, with responders defined as subjects who had a ≥ 1 - category improvement from baseline. For IGA-PN, individual items (PN Activity and PN Stage) will be presented with counts and percentages for categories by treatment group and visit; a logistic regression analysis will be performed for PN Activity at Week 14, with

responders defined as subjects who had a ≥ 1 -category improvement from baseline. For PBI-P, the count and percentage of responders (defined as those with a PBI-score of ≥ 1 at Week 14) will be presented by treatment group. For open-label extension period visits, descriptive statistics will be displayed by treatment for all secondary variables.

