8.5.1.2 Mixed model repeated measures analysis

A mixed model repeated measures analysis using ‘direct likelihood’ will be performed for continuous efficacy outcomes. The SAS procedure PROC MIXED will be used. The preferred model will include the fixed effects of treatment, visit, treatment-by-visit interaction, and the baseline value of the endpoint variable as a covariate. An unstructured matrix for the variance-covariance will be used. The denominator degrees of freedom will be calculated according to the Kenward-Roger method.

In case of non-convergence of the preferred model or memory issues, the following back-up models are defined:

1. The same as the preferred model, but the Kenward-Roger method will be replaced by Satterthwaite approximation.

2. The same as the preferred model, but with handling of the selection of the covariance structure for the final model in a hierarchical fashion, with the order being Toeplitz, AR (1), and compound symmetry, respectively.

The second back-up model will only be used if the first back-up model does not converge or has memory issues.

The model will provide least-squares mean estimates, standard errors, two-sided 95% confidence intervals and p-values (where applicable) for mean change at all visits between treatments (NAL ER vs. placebo).

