8.6.3 Analysis of secondary efficacy endpoints

All secondary endpoints will be analyzed using the mITT population.

MMRM without imputation for missing data:

The following secondary efficacy endpoints will be analyzed using a mixed model for repeated measures (MMRM):

- The mean change in 7-day average WINRS from baseline to Week 14 for the NAL ER treatment arm versus the placebo arm;
- The mean change in ItchyQoL from baseline to Week 14 for the NAL ER treatment arm versus the placebo arm;
- The mean change in sleep disturbance (PROMIS Sleep Disturbance Short Form 8a) from baseline to Week 14 for the NAL ER treatment arm versus the placebo Arm.

The analysis of change from baseline to week 14 will be performed utilizing all observed data for visits up to and including Week 14, without imputation for missing data. The model used for this analysis will include the fixed effects of treatment, visit, treatment-by-visit interaction, and baseline value. An unstructured variance-covariance matrix will be used in the analyses. The comparison of interest is the treatment difference at Week 14. The model will provide least-squares mean estimates, standard errors, two-sided 95% confidence intervals and p-values for mean change at all time points between treatments (NAL ER vs. placebo) for ItchyQoL (total score and subscales: symptoms, functional limitations, emotions) and PROMIS. The same statistics will be provided for WI-NRS, except for the p-values.

Sample SAS code:

```
PROC MIXED data=xxxx;
  CLASS visit treatment subjid;
  MODEL CHG = treatment visit treatment*visit baseline/solution DDFM=KENWARDROGER;
  REPEATED visit / type=un subject=subjid;
  LSMEANS treatment*visit / pdiff CL;
  ODS output Diffs=outdata1 LSMeans=outdata2;
RUN;
```

Sensitivity analyses: MMRM with imputation for missing data

We will use the imputation methods described above for the primary efficacy endpoints to assess the sensitivity of missing data on inference regarding the secondary endpoints. Since these are continuous measures, we will use the delta methods described above.

Summary for Categorical Endpoints:

The count and percentage will be provided for the following endpoints:

- Change in PAS as assessed by the percentage of subjects having a 1-category improvement in the percentage of prurigenous lesions with excoriations/crusts (item 5a) from baseline to Week 14 for the NAL ER treatment arm versus the placebo arm;

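### The MMRM for ItchyQoL, PROMIS sleep and mean WI-NRS change fits one baseline slope to all visits; a baseline-by-visit term would protect the Week 14 contrast at almost no cost

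*Protocol*

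**What the plan says.** Protocol 13.4.6.2 analyses change from baseline in WI-NRS, ItchyQoL and PROMIS sleep with an MMRM that "includes the fixed effects of treatment, visit, treatment by visit interaction, and baseline value". The comparison of interest is at Week 14.

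SAP 8.5.1.2 gives the same terms: "treatment, visit, treatment-by-visit interaction, and the baseline value of the endpoint variable as a covariate". It adds: "An unstructured matrix for the variance-covariance will be used". SAP 8.6.3 repeats the list and supplies the code: "MODEL CHG = treatment visit treatment*visit baseline/solution DDFM=KENWARDROGER". The main analysis is run "utilizing all observed data for visits up to and including Week 14, without imputation for missing data".

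No baseline-by-visit term appears in either document. The PROC MIXED step for imputed data in SAP Appendix 12.3 has none either. The imputation regressions in that appendix are fitted visit by visit, so they do not impose a common slope. ItchyQoL and PROMIS contribute Weeks 6, 10 and 14; WI-NRS adds Week 2.

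**The concern.** The model lets the treatment effect and the residual covariance vary freely by visit, but holds the regression on baseline identical at all of them. The shared slope is a weighted average that leans towards visits with smaller residual variance. If those are the early visits and the slope changes over time, the fitted slope is wrong at Week 14, the visit that is tested.

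With complete data, randomisation keeps the contrast unbiased and only precision suffers. With missing data the analysis depends on a correct mean model. A wrong slope then biases the contrast if the subjects still observed at Week 14 differ in mean baseline between arms.

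Unequal dropout is a realistic planning case. Protocol 13.1 implies TR03 completion of 12 of 18 on NAL ER 162 mg and 20 of 22 on placebo. ItchyQoL and PROMIS are second and fourth in the fixed sequence of Protocol 13.4.6.3.

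**Working it through.** **The plan's own figure.** Neither document states a power, SD or effect size for these endpoints. The only design figure is for the primary endpoint (25% v 45%, two-sided 0.05, 90% power):

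n per arm = [1.96√(2×0.35×0.65) + 1.2816√(0.25×0.75 + 0.45×0.55)]² / 0.20² = (1.322 + 0.845)² / 0.04 ≈ 117.4, so 118 per arm or 236 in total.

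This agrees with the SAP's 234 without site and the planned 240. It does not bear on the MMRM.

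**Assumptions for what follows (none is in the documents).** Units are baseline SDs. Visits are Weeks 6, 10 and 14, with residual SDs 0.70, 0.85 and 1.00, within-subject correlation 0.6 and no true effect. The slopes of change on baseline are:
- equal: −0.40 at every visit
- moderate change: −0.25, −0.40, −0.50
- strong change: −0.10, −0.35, −0.60

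**Precision with complete data.** The Week 14 estimate is the difference in mean outcome minus b times the difference in mean baseline. Its variance is (2/n)(S₃₃ + d²·Var B), with d = b₁₄ − b. The standard error therefore exceeds that of the visit-specific model by √(1 + d²·Var B/S₃₃), where here Var B = S₃₃ = 1. Generalised least squares weights 1′S⁻¹/(1′S⁻¹1) are about 0.72, 0.26 and 0.02, so Week 14 hardly informs the shared slope.
- Moderate: b = 0.72(−0.25) + 0.26(−0.40) + 0.02(−0.50) = −0.294; d = −0.206; √1.042 = 1.021.
- Strong: b = 0.72(−0.10) + 0.26(−0.35) + 0.02(−0.60) = −0.175; d = −0.425; √1.181 = 1.087.
- Equal: d = 0; ratio 1.

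Simulation with no missing data gave 1.021, 1.087 and 1.000, with no bias. A separate calculation, with baseline correlations falling from 0.45-0.65 at Week 6 to 0.25-0.50 at Week 14, gave variance ratios of 1.004-1.024. The standard error is then 0.2-1.2% larger.

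**Bias with dropout.** Both models were fitted by maximum likelihood to 400,000 simulated subjects, with standard errors rescaled to 360. Dropout was 33% on NAL ER (6/18) and 9% on placebo (2/22), depending on baseline in the NAL ER arm only. Simulation error of the bias is about 0.004.

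| Slopes | Log-odds ratio of NAL ER dropout per baseline SD | Bias, common slope | SE, common slope | Bias/SE | Bias, visit-specific | SE, visit-specific |
|---|---|---|---|---|---|---|
| Equal | 1.0 | 0.007 | 0.117 | 0.06 | 0.006 | 0.118 |
| Moderate | 0 | 0.001 | 0.120 | 0.01 | 0.001 | 0.117 |
| Moderate | 0.5 | 0.032 | 0.120 | 0.27 | −0.002 | 0.118 |
| Moderate | 1.0 | 0.053 | 0.120 | 0.44 | −0.003 | 0.118 |
| Strong | 0.5 | 0.060 | 0.128 | 0.46 | −0.006 | 0.118 |
| Strong | 1.0 | 0.121 | 0.128 | 0.95 | 0.004 | 0.118 |

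As a rough check, bias ≈ d × (difference in mean baseline between arms among those observed at Week 14). For a log-odds ratio of 1.0, moderate slopes give −0.21 × −0.271 = 0.057 and strong slopes −0.43 × −0.277 = 0.119, against 0.053 and 0.121 simulated.

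A smaller simulation (400 trials per scenario, dropout about 29% and 8%) gave biases of 0.031, 0.015 and 0.032 against standard errors of 0.111, 0.108 and 0.120, or 0.14-0.28 SE.

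**When there is no bias.** With equal slopes the bias is within simulation error, as the first table row shows. With strong slope change but the same dropout rate (20%) and the same dependence on baseline in both arms, it was −0.002.

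**Effect on the test.** Two-sided error is Φ(−1.96+k) + Φ(−1.96−k):
- k = 0.27: 0.0455 + 0.0129 = 5.8%
- k = 0.44: 0.0643 + 0.0082 = 7.2%
- k = 0.95: 0.156 + 0.002, about 16%

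In these scenarios more severe NAL ER subjects leave and slopes steepen, so the bias is against NAL ER and the chance of a false claim of benefit falls below 2.5%. If milder subjects left instead, the direction would reverse.

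**The case against.** The model is a standard, consistently prespecified MMRM, and the documents contain no evidence that the slopes change. A reader might infer that precision is lost in any case, that baseline-dependent NAL ER dropout alone biases the result, or that the 0.05 level is not held. None of these follows. Each needs slopes that differ by visit, and bias also needs dropout that leaves the arms with different mean baselines.

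Nor do falling baseline-to-visit correlations prove that slopes change. A constant slope of 0.5 (score on baseline) with residual SDs of 0.70 and 1.00 gives 0.5/√(0.25+0.49) = 0.58 at Week 6 and 0.5/√(0.25+1) = 0.45 at Week 14, with no misfit.

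The plan also limits the damage:
- Protocol 9.6 asks discontinuers to return for the planned Week 14 visit, and Protocol 13.1 expects better retention than in TR03.
- SAP 7.4.1 and 8.6.3 add control-based and tipping-point imputation. Once outcomes are completed by visit-specific regressions, the common slope no longer creates dropout bias.
- For WI-NRS, SAP 8.6.3 reports no p-value. Entry requires a mean of at least 7 on a 0-10 scale (Protocol 9.5.1), so the narrow baseline range keeps any bias small in points.
- The confirmatory role of ItchyQoL and PROMIS is unsettled. The SAP's multiplicity list puts them seventh and eighth of nine, while SAP section 9 says they left the ranking.

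All of this stands and sets the severity low. It does not remove the restriction from the main analysis. The sensitivity analyses make different assumptions about the missing data and do not correct the main estimate.

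**Conclusion.** The point holds as a conditional, low-severity improvement. The restriction is real and identical in Protocol and SAP.

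If slopes vary by visit, the Week 14 standard error is about 0-2% larger under moderate change and up to about 9% larger under strong change. If dropout also depends on baseline differently by arm, bias is about 0.1-0.4 standard errors in moderate scenarios and about 0.9 in the extreme one, in either direction. It is nil when slopes are equal or the dropout pattern is the same in both arms.

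These sizes rest on assumed slopes, residual SDs, correlation and strength of dropout dependence, and on TR03-like dropout counted as missing at Week 14. The Week 14 return visit should make actual missingness smaller. The documents do not support saying that the planned analysis is biased or that its error rate is inflated; they support only that it is open to both under conditions that the plan neither rules out nor needs to accept.

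**What to change.** Add the interaction in four places: Protocol 13.4.6.2, SAP 8.5.1.2, the text and code in SAP 8.6.3, and the PROC MIXED step for imputed data in SAP Appendix 12.3. The model statement becomes `CHG = treatment visit treatment*visit baseline baseline*visit`.

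The cost is two extra parameters for ItchyQoL and PROMIS and three for WI-NRS, with 360 subjects. When slopes are equal the standard error is essentially unchanged (0.117 v 0.118 in the first table row). If treatment codes are already open, keep the planned model as the main analysis and report the interaction model as a labelled sensitivity analysis.
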